1. PROTOCOL SUMMARY

Title:

FiO₂ Closed-Loop Control Using the ZOLL 731 Series Ventilator.

Précis:

A randomized, multicenter trial involving critically-ill patients comparing conventional, manual control of inspired oxygen (FiO₂) within a target range, with a computer-controlled, closed-loop FiO₂ delivery using an FDA-cleared continuous ventilator.

Objectives:

The objective of this study is to demonstrate that physiologic closed-loop control (PCLC) is at least as safe and effective as manual control in keeping hemoglobin oxygen saturation (SpO₂) within the target range of 92 to 96%.

The primary efficacy outcome is the relative duration as defined by the total duration of minutes with SpO₂ within the target range of 92 to 96% divided by 720 minutes (the planned duration of the study). Similarly the relative duration for the primary safety outcome is defined as the total duration of time that the SpO₂ level at or above 88% divided by 720 minutes.

Hypothesis:

We plan to conduct a 2-state statistical test: non-inferiority followed by a superiority test. Demonstration of non-inferiority for both the effectiveness and safety endpoints is required for study success.

Primary effectiveness for non-inferiority: The use of PCLC to maintain oxygen saturation (SpO₂) within the target range of 92 to 96%, as measured by the relative duration, is not inferior to the manual control (MC).

Secondary effectiveness for non-inferiority: The use of PCLC to maintain oxygen saturation (SpO₂) within the target range of 92 to 96% when FiO₂ > 21% and SpO₂ ≥ 92% when FiO₂ = 21%, as measured by the relative duration, is not inferior to the manual control (MC) group.

Primary effectiveness for superiority: The relative duration of time with SpO₂ within the target range of 92 to 96% is greater in the PCLC compared with manual control (MC) group.

Secondary effectiveness for superiority: The relative duration of time with SpO₂ within the target range of 92 to 96% when FiO₂ > 21% and

SpO₂ ≥ 92% when FiO₂ = 21%, as measured by the relative duration, is greater in the PCLC compared with manual control (MC) group.

[figure not shown]
Primary safety: The use of PCLC to maintain the SpO₂ level at or above 88%, as measured by relative duration of time, is not inferior to the manual control (MC).

Population:

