Progressive lung dysfunction in this patient population may be difficult to diagnosis within the 12-hour study period. Increased neutrophilia, defencins, and other inflammatory responses may lead to increased lung permeability. The current protocol is clear on how to proceed. If there is a sustained increase in FiO_2 without an increase in O_2 saturation, then the subject will be evaluated by the clinical team and other diagnostic measures will be employed: chest x-ray, ultrasound, CT scan to assist in understanding the sustained desaturation.

Progressive lung dysfunction may occur in the presence of pneumothorax, pneumonia, pulmonary embolism or other condition(s) directly related to the subject's traumatic injuries. We anticipate that if progressive lung dysfunction does occur, FiO₂ will be maximized to ensure oxygen saturations above the 92% level. In addition, subjects will be evaluated by the clinical team at the institution to determine any additional diagnostic or therapeutic measures, such as CT scan, PEEP, anticoagulant therapy, etc.

In cases where the FiO₂ cannot be titrated from 1.0, the subject will continue in the manual control but the data will not be used because an FiO₂ of 1.0 will not inform the study.

Delay of treatment of a condition that causes desaturation is unlikely to occur in this patient population. Subjects will be cared for in a 2:1 ratio with an ICU nurse and a respiratory therapist. Symptoms of sustained hypoxia will be noted immediately and strategies employed to treat the hypoxemia will be employed, even in the absence of a specific diagnosis. Pulmonary embolism, pneumonias or pneumothorax will be readily diagnosed with diagnostic radiological tests.

Ventilator risks:

There are known risks associated with all ventilatory strategies. These are well known and characterized in the 731 Operation Manual. The PCLC adapted Operation Manual also includes specific information on the operation and management of the device during PCLC operation. There are no unanticipated ventilator-centric risks associated with this protocol.

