The closed-loop control system includes both audible and visual alarms to alert the clinician of an unreliable signal from the pulse oximeter, malposition of the pulse oximeter sensor, and subject SpO₂ less than 88%. Details of these alarms are documented in Appendix B which is taken from the Operation Manual. All alarms and low SpO₂ conditions will be recorded automatically on the laptop computer data logger.

If the subject requires a procedure in the ICU that the standard of care requires an increase in FiO₂ to 1.0 (e.g. bronchoscopy) the data collection will automatically continue but such data will

not be considered in the statistical analysis because such procedures are not part of the trial protocol. The Case Report Form will capture such events and note the times that such procedures began and were completed. Data inclusion in the statistical analysis will resume once FiO₂ control returns to the trial protocol. If the subject requires transfer to the operating room, radiology for treatment or some other non-ICU location, data collection will not be included in the statistical analysis until the subject returns to the ICU. These incidents outside of the ICU will also be captured on the Case Report Form. The goal of the study will be to have a minimum of 12 hours of data collection for each subject in either arm of the study

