5.5 Strategies for Recruitment and Retention

There will be no compensation to subjects for study participation.

We anticipate subject participation not to exceed 24 hours of data collection (to produce 12 hours of evaluable data) for the entire study; however subjects will be monitored for adverse events for 24 hours following the end of the intervention. Subjects will be terminated from the study after the 24 hour period ends.

We have chosen the four Level 1 trauma units to maximize recruitment of a study population that meets all of the inclusion criteria. Each trauma unit admits approximately 85 trauma patients/year that would be eligible for this study and we plan to recruit equal numbers of subjects from each trauma unit. If this is not feasible, no more than 60% of the total subjects will come from a single study site.

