12.2 Statistical Analysis

For the primary outcomes, the intent-to-treat (ITT) population will be used for all efficacy and safety analyses. All subjects that were randomized and started the assigned ventilation strategy protocol will be included in the ITT. All summary tables for quantitative parameters will display mean, standard deviation, median, interquartile range, and range (minimum and maximum), as well as number of missing data (if relevant). All summary tables for qualitative parameters will display counts, percentages and number of missing data if relevant. Baseline characteristics will be described using the ITT population. Demographics, medical history and other baseline variables will be summarized as appropriate to the type of data. The primary effectiveness outcome will be defined as the proportion of time during the 12 hour monitoring period that the subject's SpO₂ levels were within the target range relative to the actual total monitoring time (which is targeted to be 12 hours for all subjects). By using the proportion of time instead of the actual time, we are able to normalize the outcome based on the total amount of monitoring time available. We will assess normality of the response variables within each of the two groups by visual inspection of the histograms and box plots and by performing the test for normality of data using the Shapiro Wilk test. If the assumption of normality for the primary effectiveness outcome does not seem tenable, we will use the arcsine square root transformation which is recommended to normalize skewed percentage data. A one-sided lower 97.5% confidence interval will be calculated for the difference between the two monitoring strategy groups (PCLC minus MC) in terms of the effectiveness outcome (duration where SpO₂ remains between 92 and 96% relative to the total monitoring time) and the lower limit will be compared to the noninferiority margin of 0.12. Similar analyses will be conducted for the secondary effectiveness outcome with the only difference being the way the duration is calculated for the secondary effectiveness outcome. For this analysis, the target duration will be calculated as amount of time that SpO₂ remains between 92 and 96% when FiO₂ > 21% and SpO₂ ≥ 92% when FiO₂ = 21%. The safety outcome (duration where SpO₂ remains above 88% relative to the total monitoring time) will be assessed using a one-sided lower 97.5% confidence interval and the lower limit will be compared to the non-inferiority margin of 0.004. If non-inferiority is established for an endpoint, we will proceed in conducting a superiority test and will compare the lower confidence limit to 0.

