
For the analysis of secondary safety outcome, data point estimates will be reported with 95% confidence intervals followed by a Fisher's Exact Test at the 5% level of confidence. Specifically the percentage of subjects reporting at least one adverse event (i.e serious, any device related, etc.) will be calculated for each group and compared using Fisher's Exact Test. The relative risk of each adverse event with the corresponding two-sided 95% confidence interval will be presented.

Missing data: The primary analysis is an intent to treat analysis. In order to minimize the possibility of missing data, the total duration of monitoring will be extended for each subject as needed in order to collect at least 12 hours of evaluable data. As a sensitivity analysis, the primary outcome measure also will be calculated as the relative time the subject was on target compared to the total amount of time they were on manual or closed-loop control. Therefore each subject should have the outcome measurement. The amount of missing data is expected

to be low based on past experience with subject retention. However there is a very low probability that some subjects may die before completing 12 hours of monitoring on the device. In this case, the relative duration will be derived by using the total duration of time the subject was on target relative to the monitoring time until they died. If a subject does not have 12 hours of monitoring data on the device due to a reason other than death, we will conduct sensitivity analysis by assuming different scenarios. In a worst case scenario, the primary outcome will be computed as the total time in the target range divided by 720 minutes. In a best case scenario, the primary outcome will be computed as the total time in the target range divided by the total amount of time the subject was observed (i.e. <720 minutes). In the event of missing data on the primary safety and efficacy outcomes (except where the subject died), the reason for the missing values will be explored, and the pattern of missing values (e.g. missing at random, missing completely at random) will be evaluated. In addition, analyses excluding those subjects without 12 hours of monitoring will also be conducted as sensitivity analyses.

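### Section 3.3 discards data from subjects whose FiO2 cannot be brought down from 1.0; this post-randomisation, oxygenation-related exclusion conflicts with the ITT rule in section 12.2, which never mentions it

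*Combined protocol and SAP*

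**What the plan says.** Section 3.3 discusses progressive lung dysfunction during the 12-hour study period. Where FiO2 cannot be titrated from 1.0, it says that "the subject will continue in the manual control but the data will not be used", on the ground that such an FiO2 tells the study nothing. It does not say whether the data are the whole record or only the minutes at 1.0, which arm or endpoint is meant, or how long the state must last.

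Section 12.2 applies the ITT population to all efficacy and safety analyses of the primary outcomes: "All subjects that were randomized and started the assigned ventilation strategy protocol will be included in the ITT". The effectiveness outcome is a proportion "relative to the actual total monitoring time (which is targeted to be 12 hours for all subjects"). Section 1 instead defines it as time "within the target range of 92 to 96% divided by 720 minutes (the planned duration of the study"). On missing data, 12.2 says that "the total duration of monitoring will be extended for each subject as needed in order to collect at least 12 hours of evaluable data" and concludes: "Therefore each subject should have the outcome measurement". Section 5.5 caps participation at "not to exceed 24 hours of data collection (to produce 12 hours of evaluable data").

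Section 4.3 removes two kinds of time from the analysis. One is time in ICU procedures for which the standard of care requires FiO2 1.0, which will "not be considered in the statistical analysis because such procedures are not part of the trial protocol". The other is time outside the ICU.

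**The concern.** A subject reaches FiO2 1.0 and stays there after randomisation, under the assigned strategy, because oxygenation is poor. Removing data on that trigger selects on something close to the outcome. The selection need not be equal in the two arms, because FiO2 is set by the algorithm in one and by the treatment team in the other.

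The safety endpoint is the more exposed. It counts time below 88%, and a subject who desaturates although FiO2 is already 1.0 is a case it exists to record. The sponsor's reason, that such time says nothing about the controller, may suit a question about controller performance. It does not suit a safety comparison of randomised strategies.

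Section 1 requires non-inferiority on both endpoints for study success. Two analysts following these documents could build different primary datasets, and the choice could be made after the data are seen.

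**Working it through.** **Side by side**

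- Whole record dropped: the subject was randomised and started the strategy, so 12.2 places the subject in the ITT set and expects an outcome value. Section 3.3 leaves none. This is a direct contradiction.
- Minutes dropped: the subject stays in the ITT set, but recorded monitoring time leaves the denominator defined in 12.2. It is neither procedure time nor out-of-ICU time, so 4.3 does not cover it. Since evaluable is undefined, later minutes might take its place under the extension rule.
- Withdrawal: section 5.4 excludes patients who cannot hold 88% at FiO2 100%, and 5.6.2 lets the investigator end participation if a criterion is newly met. Neither gives a data rule. A subject holding 90% at FiO2 1.0 falls under 3.3 but not under 5.4.
- Missing-data text: 12.2 offers sensitivity scenarios for subjects without 12 hours of data. Here SpO2 has been recorded (4.3) and is then set aside.

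**The plan's own figure.** Inputs from 12.1.1: margin 0.12, SDs 0.33 and 0.23, one-sided 2.5%, true difference zero. With 91 per group, SE = sqrt((0.33² + 0.23²)/91) = 0.0422, and power = Phi(0.12/0.0422 - 1.96) = 81%. The stated 91 for 80% reproduces closely.

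**Safety illustration.** The frequencies are assumed, because the documents give none. The 0.004 margin (12.1.2) over 105 subjects of 720 minutes is 0.004 × 720 × 105 = 302 subject-minutes. If one arm loses k more subjects than the other, each with x minutes below 88%, and the remaining subjects average m, the difference shifts by k(x/720 - m)/105. The preliminary means in 12.1.2 give m = 0.002 to 0.004.

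| k | x (min) | Shift | Share of 0.004 |
|---|---|---|---|
| 1 | 15 | 0.00016-0.00018 | 4-4.5% |
| 3 | 30 | 0.0011 | 27-28% |
| 5 | 60 | 0.0038-0.0039 | 94-97% |

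The last row is extreme. The manual-control mean in 3.2.2 is 1.25 minutes per 4 hours, or 3.75 per 12 hours, and 60 minutes is 16 times that.

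**Efficacy illustration.** Take an arm mean of 0.30 (12.1.1) and lost subjects with no in-range time. One moves the mean by 0.30/105 = 0.0029 (2.4% of 0.12). Five move it by 0.0143 (12%).

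**Direction within one subject.** Suppose 240 of 720 minutes are at FiO2 1.0, and 240 of the other 480 are in range. If none of the FiO2 1.0 time is in range, dropping it raises the score from 240/720 = 0.33 to 240/480 = 0.50. If all of it is in range, dropping it lowers the score from 480/720 = 0.67 to 0.50.

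**The case against.** The strongest reply is that this will seldom happen and will matter little when it does. Section 3.3 calls increased desaturation from progressive lung dysfunction under closed-loop titration rare, 5.4 screens out the worst cases at entry, and 3.3 expects FiO2 to be maximised to keep SpO2 above 92%. That stands as a limit on size. It does not reconcile the two rules, and the safety margin is small enough for a few subjects to count.

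It can also be said that 12.2 uses a proportion precisely to normalise for available time, so dropped minutes fit its method, and that its sensitivity analyses would catch a subject left short of 12 hours. The first part is fair as mechanics, but nothing in 12.2 authorises the removal. The second concerns sensitivity analyses and leaves the primary dataset undefined.

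Stronger readings are tempting, and the documents do not support them:

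- A reader might infer that the clause favours closed-loop control. Losing poor data only from that arm would do so; losing it only from the manual arm would do the reverse. Nothing shows which is likelier.
- A reader might take the porcine study in 3.2.2 as a measure of size, since in-range time rose from 64% to 73% when values with FiO2 at extremes were left out. The readable text does not define the extremes, which may include low FiO2, so this is not shown to be the same kind of exclusion.
- A reader might conclude that later minutes will replace the lost ones. That is only possible, and a subject who stays at 1.0 may have no better minutes to offer.
- A reader might think that time after a move to manual control belongs to no arm. The ITT rule already assigns it to the randomised arm, and 4.3 permits clinician override.
- The 720-minute and actual-time denominators disagree even without this clause. That is a separate matter.

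**Conclusion.** The clause is wrong as written and should be corrected. Following it would breach the ITT rule or remove recorded time that 12.2 counts, and it could discard desaturation that the safety endpoint is there to measure. No other section resolves this.

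Its effect in this trial cannot be sized from the documents. It is negligible for safety if SpO2 holds at or above 88% at FiO2 1.0, and only an extreme imbalance approaches the whole safety margin. Efficacy is less exposed and could move either way. The figures above rest on 105 subjects per arm, 720 minutes each, the preliminary means in 12.1 and assumed counts of affected subjects.

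**What to change.** Delete the data-discard clause from 3.3, or limit it to a sensitivity analysis. State in 12.2 that, under the existing ITT rule, recorded SpO2 time at sustained FiO2 1.0 counts in the randomised arm and in the denominator for both primary endpoints, with only the procedure and out-of-ICU exceptions of 4.3. Pre-specify a sensitivity analysis for both endpoints that excludes this time, saying whether it drops minutes or whole records. Report affected subjects and minutes by arm. Sections 3.3 and 4.3 must also be reconciled on what continuing in manual control means for a closed-loop subject; no clinical rule is proposed here.

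No new data are needed, because SpO2 is recorded throughout. There are two statistical costs.

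1. Dilution. Manual-control time counted in the closed-loop arm pulls the difference towards zero, which is anti-conservative for non-inferiority. If five closed-loop subjects spend 360 minutes each in manual control and then perform like the manual arm, that is 5 × 360/(105 × 720) = 2.4% of the arm's time. A true deficit of 0.120 then appears as 0.117. With SE = sqrt((0.33² + 0.23²)/105) = 0.0393, the one-sided error becomes 1 - Phi(1.96 - 0.00286/0.0393) = 3.0%. Time with FiO2 fixed at 1.0 in either arm also dilutes. The sensitivity analysis addresses this.
2. A wider safety interval if prolonged desaturation occurs. Assume that the four-hour SDs in 3.2.2 (2.64/240 = 0.0110 and 1.37/240 = 0.0057) hold for 12 hours, and that the true difference is zero. The SE with 105 per arm is then 0.00121, and power against 0.004 is about 91%. Adding affected subjects to each arm gives SE 0.00131 and power about 86% (one with 30 minutes below 88%), 0.00148 and 77% (three with 30 minutes), or 0.00218 and 45% (three with 60 minutes, an extreme case).

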3.4 Potential Benefits

One potential benefit to participants is the constant equilibration of oxygen saturation to remain within the physiologic target range of 92 to 96%, preventing exposure to excessive inspired O₂ levels while at the same time preventing transient hypoxemia.

Another potential benefit will be the ability to prevent hyperoxemia, by keeping the SpO₂ within the target range.

4. STUDY OBJECTIVES

The specific objective of this IDE clinical study is to test a physiologic closed-loop algorithm which will continuously adjust the level of inspired oxygen concentration (FiO_2) of a mechanical ventilator using physiologic closed-loop control (PCLC) to maintain a target level of hemoglobin oxygen saturation (SpO_2) based on readings from a pulse oximeter in critically ill patients in the Surgical ICU. Results from the study will be applicable to patients in the hospital and in the prehospital environment as well as during transport. The 731 Series ventilator used in the study is identical to the FDA-cleared device (K071526, K091238, K103318, K111473) except that the software has been revised to support include FiO_2 control algorithm. In addition, the military has approved the device for use in all military ground and air transport vehicles.

4.1 Primary Objective

The primary effectiveness objective is to demonstrate that use of PCLC is not inferior to the manual control in keeping hemoglobin oxygen saturation (SpO_2) within the target range of 92 to 96% while the primary safety objective is to demonstrate that the use of PCLC is not inferior to the manual control in maintaining the oxygen saturation (SpO_2) at or above 88% level.

4.1.1a Primary effectiveness variable:

To assess the relative duration of time with SpO_2 between 92 and 96% (inclusive) during the study period.

4.1.1b Secondary effectiveness variable:

To assess the relative duration of time with SpO_2 between 92 and 96% (inclusive) when $\text{FiO}_2 > 21\%$ and $\text{SpO}_2 \geq 92\%$ when $\text{FiO}_2 = 21\%$.

4.1.2a Primary effectiveness hypothesis

The use of PCLC to maintain hemoglobin oxygen saturation (SpO_2) within the target range of 92 to 96%, as measured by the relative duration, is not inferior to the manual control (MC).

4.1.2b Secondary effectiveness hypothesis

The use of PCLC to maintain hemoglobin oxygen saturation (SpO_2) within the target range of 92 to 96% when $\text{FiO}_2 > 21\%$ and $\text{SpO}_2 \geq 92\%$ when $\text{FiO}_2 = 21\%$, as measured by the relative duration, is not inferior to the manual control (MC).

4.1.3 Primary safety variable

To assess the relative duration of time with $\text{SpO}_2 < 88\%$ during the study period.

